Once the results are available, if the subject continues to meet entrance criteria they will return for their baseline Day 1 (randomization) visit. This visit takes place about 1 to 4 weeks after the screen visit. At this visit, vital signs are recorded, 33 ml of blood will be drawn for a CBC with differential, a complete metabolic panel (CMP), and for biomarker assays (for example, GM-CSF, IFN- γ , IL-1 β , IL-2, IL-6, IL-8, IL-10, IL-12p70, TNF- α , Eotaxin, IP-10, MCP-1, MCP-4, MIP-1 β , TARC, P-Tau, Total Tau, and A β species), and tests of cognition, such as the MMSE, ADAS-cog, the ADCS-ADL scale, Trails A, Trails B, CDR, and the Mohs Cancellation task, are administered. The test article will then be delivered by the unblinded pharmacist, administered subcutaneously by the (blinded) study nurse or clinician, and the subject then goes home.

Subsequent injections will also be administered at the clinic. About 4 ml of blood will be drawn for CBC plus differential approximately every three days during the treatment phase to monitor for leukocytosis (see safety monitoring plan), and an additional 4 ml of blood will be drawn for CMPs once every week of the treatment phase. Vital signs, injection site review, and adverse events will be recorded at each visit. At the last treatment visit approximately three weeks later, we will record vitals, perform a physical exam, review for adverse events, administer cognitive tests and draw 33 ml blood for a CBC with differential, a CMP, and biomarker assays. A brain MRI will be done for comparison with the initial screen MRI to assess for any changes in the Medial Temporal lobe and for any incidence of vasogenic edema and microhemorrhage.

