Because of the extensive safety history of Leukine[®] in elderly patients, we do not anticipate any serious safety problems, but we must be vigilant in assessing safety. A review of published adverse events for GM-CSF and the Genzyme Leukine[®] Product Insert and the papers it references will be used to guide the safety monitoring protocol ([38], attached as Appendix D). The greatest safety concern noted with Leukine[®] is excessive leukocytosis. Therefore, as advised by Sanofi/Genzyme Corporation, we will obtain a CBC with differential twice a week during treatment and the dosage will be reduced by half if total ANC rises above 20,000/mm³. In addition, the DSMB described below will monitor laboratory results, the MRI and the cognitive assessments for any indications of toxicity. Following are the abbreviated categories of the National Cancer Institute's (NCI) graded toxicity protocol used by Daud et al., 2008 for assessing safety of Leukine[®] [57], although the latest version of the NCI-CTCAE (Version 4.03) will also be referenced for all AE's (attached as Appendix F):

Anemia
Lymphopenia
Pain
Fever Flu-like symptoms
Arthralgia/myalgia
Injection-site reaction
Fatigue
Abdominal cramps
GERD/indigestion Insomnia
Cough
Sweating

Data and Safety Monitoring Board (DSMB):

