Renal and Hepatic Dysfunction In some patients with preexisting renal or hepatic dysfunction enrolled in uncontrolled clinical trials, administration of LEUKINE has induced elevation of serum creatinine or bilirubin and hepatic enzymes. Dose reduction or interruption of LEUKINE administration has resulted in a decrease to pretreatment values. However, in controlled clinical trials the incidences of renal and hepatic dysfunction were comparable between LEUKINE (250 mcg/m²/day by 2-hour IV infusion) and placebo-treated patients. Monitoring of renal and hepatic function in patients displaying renal or hepatic dysfunction prior to initiation of treatment is recommended at least every other week during LEUKINE administration.

PRECAUTIONS

General Parenteral administration of recombinant proteins should be attended by appropriate precautions in case an allergic or untoward reaction occurs. Serious allergic or anaphylactic reactions have been reported. If any serious allergic or anaphylactic reaction occurs, LEUKINE therapy should immediately be discontinued and appropriate therapy initiated.

A syndrome characterized by respiratory distress, hypoxia, flushing, hypotension, syncope, and/or tachycardia has been reported following the first administration of LEUKINE in a particular cycle. These signs have resolved with symptomatic treatment and usually do not recur with subsequent doses in the same cycle of treatment.

Stimulation of marrow precursors with LEUKINE may result in a rapid rise in white blood cell (WBC) count. If the ANC exceeds 20,000 cells/mm³ or if the platelet count exceeds 500,000/mm³, LEUKINE administration should be interrupted or the dose reduced by half. The decision to reduce the dose or interrupt treatment should be based on the clinical condition of the patient. Excessive blood counts have returned to normal or baseline levels within three to seven days following cessation of LEUKINE therapy. Twice weekly monitoring of CBC with differential (including examination for the presence of blast cells) should be performed to preclude development of excessive counts.

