Pediatric Use Safety and effectiveness in pediatric patients have not been established; however, available safety data indicate that LEUKINE does not exhibit any greater toxicity in pediatric patients than in adults. A total of 124 pediatric subjects between the ages of 4 months and 18 years have been treated with LEUKINE in clinical trials at doses ranging from 60-1,000 mcg/m²/day intravenously and 4-1,500 mcg/m²/day subcutaneously. In 53 pediatric patients enrolled in controlled studies at a dose of 250 mcg/m²/day by 2-hour IV infusion, the type and frequency of adverse events were comparable to those reported for the adult population.

Liquid solutions containing benzyl alcohol (including liquid LEUKINE) or lyophilized LEUKINE reconstituted with Bacteriostatic Water for Injection, USP (0.9% benzyl alcohol) should not be administered to neonates (see WARNINGS).

Geriatric Use In the clinical trials, experience in older patients (age ≥65 years), was limited to the acute myelogenous leukemia (AML) study. Of the 52 patients treated with LEUKINE in this randomized study, 22 patients were age 65-70 years and 30 patients were age 55-64 years. The number of placebo patients in each age group were 13 and 33 patients respectively. This was not an adequate database from which determination of differences in efficacy endpoints or safety assessments could be reliably made and this clinical study was not designed to evaluate difference between these two age groups. Analyses of general trends in safety and efficacy were undertaken and demonstrate similar patterns for older (65-70 yrs) vs younger patients (55-64 yrs). Greater sensitivity of some older individuals cannot be ruled out.

Table 6

Percent of AuBMT Patients Reporting Events					
Events by Body System	LEUKINE		Events by Body System	LEUKINE	
	(n=79)	(n=77)		(n=79)	(n=77)
Body, General			Metabolic, Nutritional Disorder		
Fever	95	96	Edema	34	35
Mucous membrane disorder	75	78	Peripheral edema	11	7
Asthenia	66	51	Respiratory System		
Malaise	57	51	Dyspnea	28	31
Sepsis	11	14	Lung disorder	20	23
Digestive System			Hemic and Lymphatic System		
Nausea	90	96	Blood dyscrasia	25	27
Diarrhea	89	82	Cardiovascular System		
Vomiting	85	90	Hemorrhage	23	30
Anorexia	54	58	Urogenital System		
GI disorder	37	47	Urinary tract disorder	14	13
GI hemorrhage	27	33	Kidney function abnormal	8	10
Stomatitis	24	29	Nervous System		
Liver damage	13	14	CNS disorder	11	16
Skin and Appendages					
Alopecia	73	74			
Rash	44	38			

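### Day 1 requires no timed post-dose vital signs or observed wait after the first injection, the dose at which the product insert reports a first-administration reaction (minor)

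*Combined protocol and SAP*

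**What the plan says.** The Day 1 account in Study Events opens with "At this visit, vital signs are recorded, 33 ml of blood will be drawn for a CBC with differential", goes on to the other blood tests and the cognitive battery, and ends with the injection, which is "administered subcutaneously by the (blinded) study nurse or clinician, and the subject then goes home".

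For the treatment phase the same section says: "Vital signs, injection site review, and adverse events will be recorded at each visit". Specific Aim 1 and the study schedule agree, with one set of vital signs per treatment visit. None of the three says whether the set is taken before or after the dose. The schedule also marks adverse-event and injection-site review on Day 1.

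The Data Safety Monitoring Plan says of the Leukine insert: "Product Insert and the papers it references will be used to guide the safety monitoring protocol". That insert, reproduced at the end of the document, bears on this point in three places:

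- Precautions, General, asks for care with this class of product: "Parenteral administration of recombinant proteins should be attended by appropriate precautions in case an allergic or untoward reaction occurs".
- The same paragraph describes a syndrome of breathing difficulty, low oxygen and flushing, and gives its other signs and its timing as "hypotension, syncope, and/or tachycardia has been reported following the first administration of LEUKINE in a particular cycle". It adds that the signs cleared with treatment of symptoms and "usually do not recur with subsequent doses in the same cycle of treatment".
- Geriatric Use says: "Greater sensitivity of some older individuals cannot be ruled out".

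**The concern.** The primary aim is safety and tolerability in a population new to this drug. The insert links one reaction to the first dose, and blood pressure and pulse are what would show part of it. In the order the narrative gives, the only Day 1 set of vital signs comes before any exposure, and the participant leaves after the injection with no stated wait.

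The stake is individual protection. Participants may be up to 85 years old with MMSE 10-26, so their own later account of a faint feeling or a fast pulse is weak evidence, even though a study partner comes to the visits. The insert's trial experience at 65 and over comes from one leukemia study, with 22 treated patients aged 65-70. A change that is short or causes no symptoms would leave no record.

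**Working it through.** The plan states no figure on this point, so the check is mainly a comparison of texts, with some arithmetic on reach and exposure.

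**1. Is a post-dose reading required anywhere on Day 1?** Study Events puts the vital signs first and the injection last. Specific Aim 1 and the schedule require a set at each treatment visit without tying it to the dose. The schedule gives 1 (screen) + 15 (treatment days) + 2 (follow-ups) = 18 sets per participant, none timed to an injection. The Day 1 injection-site review implies some staff contact after the dose, but it is not timed and calls for neither blood pressure nor pulse. A post-dose reading is allowed but not required.

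**2. Can the Day 2 reading stand in for it?** The insert's Pharmacokinetics section says that after subcutaneous dosing the drug was detectable for up to six hours. A Day 2 reading taken before the second injection comes about a day after the first dose, well beyond those six hours. A Day 2 reading taken after the second injection concerns a dose at which the reaction usually does not recur. Neither replaces a first-dose reading.

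**3. Can the risk be sized?** No. The insert gives no rate, onset time or route for the reaction. It does allow a comparison of exposure in normal volunteers: mean peak concentration was 1.5 ng/mL subcutaneously against 5.0 (liquid) and 5.4 (lyophilized) ng/mL by two-hour infusion.

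- 1.5 / 5.4 = 27.8%
- 1.5 / 5.0 = 30.0%

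The subcutaneous peak is thus about 28-30% of the intravenous one. That may lower the concern, but it does not exclude a reaction by this route.

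**4. What would a change reach?**

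- Injections per participant: 5 days x 3 weeks = 15. The first dose is 1 of 15.
- Participants still to be dosed: 40 planned (Sample size considerations) - 30 reported (Update from last revision and current trial amendment) = 10, about 5 per arm if the last cohort follows the 5 and 5 pattern. The number rises if dropouts are replaced.

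**The case against.** The case against is substantial. The insert sets no observation period. Its Information for Patients paragraph even provides for use outside the hospital or office, whereas every injection here is given in a staffed clinic. Using the insert as a guide does not turn each precaution into a procedure; the plan names excessive leukocytosis as its greatest concern and builds blood-count monitoring on that. The Day 1 narrative is not a complete list, since it leaves out reviews that the schedule marks for that day, so the order it gives may not be strict.

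Experience in the trial is also reassuring. No study-related serious adverse events are reported in 30 participants. The DSMB's April 2016 report made seven recommendations, some on vital-sign data, injection-site review and hypertension, and none asked for post-dose readings. After the 30th participant finished treatment the DSMB approved continuing at the same dose.

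Finally, the remedy fits the hazard only in part. Subcutaneous levels peak at one to three hours, and a short wait ends before that.

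All of this stands, and it keeps the point minor. It does not close the gap. A serious-event count says little about brief or mild changes that nobody measured, and an incomplete narrative still leaves no text that requires the reading.

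**Conclusion.** The gap is real and minor: the plan as written need not measure a first-dose change in blood pressure, pulse or breathing before the participant leaves. This rests on reading Study Events in the order it gives, and on the insert's statement that the reaction usually does not recur within a cycle.

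A reader might infer four stronger things, none of which the documents support.

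- **That no vital signs follow the first injection.** They are recorded at every treatment visit from Day 2.
- **That the plan departs from the insert.** No standard in it is breached.
- **That the primary endpoint is undermined.** The Data Analysis Plan compares toxicity grades of adverse events, and symptoms such as fainting or breathlessness can be picked up at the Day 1 and Day 2 reviews.
- **That hypotension and syncope would not be captured**, because the list of side effects monitored for the DSMB omits them. That list names expected effects; CTCAE is referenced for all adverse events, so the list does not limit what is recorded.

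With no rate in the documents, any probability of a reaction would only restate the rate assumed, so none is given. With about 10 first doses left, the added readings can protect individuals but cannot estimate a rate or compare the arms.

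**What to change.** For the first injection only, amend Study Events and the study schedule as follows.

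1. Require an observed wait of a fixed length set by the study physician.
2. Before departure, record one post-dose set of vital signs with its clock time, labelled post-dose in the data sent to the DSMB, which has already asked for all vital-sign data.
3. State that the removal limit in the Management Criteria (above 165 systolic or 95 diastolic) applies to this reading only if confirmed on a repeat, so that the extra measurement does not cause unplanned removals.

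This is a cheap improvement. It needs amendment wording and its review, one schedule entry, one time field, and one set of readings by the staff member already giving the injection. Sets per participant rise from 18 to 19 (1/18 = 5.6%). With a 30-minute wait (an assumption), clinic time is 10 x 30 min = 300 min = 5 hours in total; 15 to 60 minutes gives 2.5 to 10 hours.

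There are three downsides. Day 1 becomes longer. A short wait covers only early reactions and not the one-to-three-hour peak, although the drug was already detectable at 15 minutes, the first sample. First-dose monitoring will also differ between the first 30 participants and the last 10 or so, equally in both arms.

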Because our first cohort of randomized participants did not show any evidence of ARIA, and because our preliminary preclinical results had demonstrated that GM-CSF rapidly reduced cerebral amyloid deposition in transgenic mouse models of AD ([2], attached as Appendix B), we then needed to determine whether Leukine was indeed affecting amyloid load in the trial's remaining two cohorts of participants (10 Leukine[®]-treated and 10 placebo). We also needed to be certain that the determination of mild-to-moderate cognitive impairment and subsequent enrollment of potential study participants was due to Alzheimer's disease with cerebral amyloid deposition, and not due to other neurological disease. Amyloid Positron Emission Tomography (PET) observations from recent AD phase 3 trials of bapineuzumab and solanezumab had illuminated that 16% to 22% of enrolled subjects diagnosed with mild-to-moderate AD based on clinical criteria, were misclassified and did not have evidence of abnormal A β pathology on retrospective analyses of PET imaging (Sevigny et al., *Alzheimer Dis Assoc Discord*, 2016; 30:1-7). Therefore, we revised the protocol again to perform PET imaging at screening visit, as a new inclusion criterion, and at the first follow-up visit, or within a week thereof depending upon scheduling availability, utilizing the FDA-approved amyloid-binding PET imaging agent, Forbetapir F18 (Amyvid[®]). However, no treatment decisions were declared would be made based on the outcome of the follow-up PET scan. Additionally, we included another brain MRI at the first follow-up visit, to further assess any evidence of ARIA at that time point. Because all of the other AD clinical trials had shown the ability to reduce cerebral amyloid, but had also shown the very serious adverse effects of ARIAs, it was imperative that we determine whether Leukine was indeed affecting amyloid load and if so, whether it was doing so safely and without evidence of ARIAs. Thus, we submitted to the FDA a revised protocol using Amyvid[®] PET imaging and received Exemption from IND regulations on July 15, 2016 (IND 131238).

Update from last revision and current trial amendment:

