Effects of Leukine[®] on mobilization of white blood cells will be determined by CBC with differential at screening, baseline Day 1 and on days 4, 6, 9, 11 and 15 of the treatment schedule (i.e. placebo or Leukine[®] at 250 mcg /m²/day/SC for 5 days/ week for three weeks), and at the 45 and 90 day follow-up visits. Vital signs, injection site review, and adverse event monitoring will be performed at each treatment visit. Complete metabolic panels (CMP) will be performed at screen, and on days 4, 9, 15, 45, and 90 days after initiation of GM-CSF treatment (Table 1 below summarizes the time-table of procedures for the entire study). The follow up MRI at the end of the treatment phase will provide information on any adverse changes in the brain, such as vasogenic edema and microhemorrhage. The DSMB will review all available data after each group of 5 Leukine[®]-treated and 5 placebo subjects have finished the treatment phase and determine whether the remainder of the subjects (5 Leukine[®]-treated and 5 placebo) will continue to receive the same full recommended dose (250 mcg/m²/day/SC).

HYPOTHESIS 1. Recombinant human GM-CSF, Leukine[®], will be tolerated by, and safe to use in mild-to-moderate AD patients.

SPECIFIC AIM 2. To test the hypothesis that Leukine[®] treatment will improve cognition in mild-to-moderate AD patients (*Secondary Endpoint*).

A battery of cognitive tests will be performed at baseline and at approximately 15, 45, and 90 days after initiation of Leukine[®] treatment to determine whether any AD features reverse during or after Leukine[®] treatment compared to subjects receiving placebo. Primary cognitive tests will include the Mini Mental State Examination (MMSE) and the ADAS-cog (Alzheimer's Disease Assessment Scale-cognitive subscale).

HYPOTHESIS 2. Leukine[®] treatment in adults with mild-to-moderate AD will improve cognition as measured primarily by MMSE total score and ADAS-cog total score.

SPECIFIC AIM 3. To investigate whether Leukine[®] treatment has an effect on Medial Temporal Lobe Atrophy (MTA) in mild-to-moderate AD patients (*Tertiary Endpoint*).

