Atrophy in the Entorhinal cortex (ERC) and Hippocampus (HPC), measured on MRI scans, predicts future cognitive decline and conversion to AD among individuals with Mild Cognitive Impairment (MCI). Severity of MTA, assessed with MRI scans, is strongly associated with severity of medial temporal lobe degenerative pathology, especially the severity of neurofibrillary pathology, at autopsy.

HYPOTHESIS 3. Leukine[®] treatment in adults with mild-to-moderate AD will reverse or stop the progression of MTA.

EXPLORATORY AIM 1. To assess whether Leukine[®] treatment will improve specific cognitive domains in mild-to-moderate AD patients.

A battery of cognitive tests will be performed at baseline Day 1 and at approximately 15, 45, and 90 days after initiation of Leukine[®] treatment to determine whether any AD features reverse during or after Leukine[®] treatment compared to subjects receiving placebo. Secondary cognitive domain tests will include the ADCS-ADL (Alzheimer's Disease Cooperative Study Activities of Daily Living Inventory), Trail making tests (TRAILS) A, TRAILS B, Clinical Dementia Rating (CDR), and the Mohs Cancellation Task.

EXPLORATORY HYPOTHESIS 1. Leukine[®] treatment in adults with mild-to-moderate AD will improve specific cognitive domains as measured by the ADCS-ADL, TRAILS A,

TRAILS B, CDR, and the Mohs Cancellation Task.

EXPLORATORY AIM 2. To examine the effects of Leukine[®] treatment in mild-to-moderate AD patients on biomarkers associated with AD .

Biomarkers from peripheral blood collection include various forms of the hallmark proteins that form amyloid plaques in AD (i.e. amyloid-beta [A β] peptides), as well as other proteins which levels are known to be altered in AD (hyper-phosphorylated Tau and various inflammation-associated cytokines and chemokines).

EXPLORATORY HYPOTHESIS 2. Leukine[®] treatment in adults with mild-to-moderate AD will induce changes in blood biomarkers toward published control levels.

EXPLORATORY AIM 3. To determine if Leukine[®] treatment will change amyloid load in mild-to-moderate AD patients.

Amyloid PET scans will be performed using Pittsburgh Compound B (¹¹C-PiB), produced at the UCD-Anschutz Medical Campus (AMC) cyclotron laboratory, which allows for amyloid-beta neuritic plaque density imaging, and will be used to test the hypothesis that Leukine[®] treatment of mild-to-moderate AD subjects reduces cerebral amyloid load.

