Group comparisons of changes in regional volumes and thicknesses will be analyzed using a series of one-way analyses of variance (ANOVAs). The Scheffé post hoc procedure will be used to examine differences between means; Pearson product-moment correlation coefficients evaluated the strength of relationships between of changes in regional volumes and thicknesses and cognitive measures. Receiver operator curve analyses will determine sensitivity and specificity of various MTA cut points for distinguishing between diagnostic groups. Hazard ratios (HRs) for specific predictors of MTA progression and regression will be calculated using a three-state Markov model in continuous time. The proportional intensity model will be used to analyze effects of covariates on HRs.

Exploratory Aim 2: Levels of AD-associated biomarkers in blood will be compared between placebo controls and Leukine® treatment groups. The identification of circulating biomarkers in AD is a relatively new field, with inconsistent biomarker level results reported as increased, decreased, or unchanged between studies [37]. These mixed results mean that standardized levels for AD-associated circulating biomarkers have yet to be established. Therefore, we will compare observed biomarker levels from our project to other published levels to explore whether any similarities are observed. This comparison, as well as our own results, will add to the AD-associated blood biomarker field of literature.

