A summary of all study events are presented in Table 1. All interviews with subjects and potential subjects will be carried out in a private room. At the initial visit (screen), after informed consent is obtained, the MMSE is performed. If the subject qualifies on the MMSE entry criteria then vital signs are recorded, an ECG and a physical exam are performed, and 8 ml of blood is drawn for a CBC with differential, and a complete metabolic panel (CMP). A brain MRI will also be done during the screening period to exclude other causes of dementia and to assess for Medial Temporal Lobe Atrophy (MTA). Also, the first positron emission tomography (PET) scan, using ¹¹C-PiB, will be performed during the screening period to assess evidence of cerebral amyloid load. If the PET scan is performed on the same day as the MRI scan, the PET scan will be performed after the MRI scan. A qualitative read of the ¹¹C-PiB PET scan will be made to determine evidence of β -amyloid neuritic plaques. For women enrolled, who feel that there is a chance they may be pregnant, a pregnancy test will be administered. Clinically, if the patient cannot name their last menstrual period or is uncertain whether they are pregnant or not, a urine dipstick test is performed. The creatinine level from the CMP will also

be used to assess the Glomerular Filtration Rate (GFR). Also a list of all patient medications will be recorded. Patients will have to meet the inclusion/exclusion criteria (stability on AD medications for 2 months prior to screen and all other meds must be stable 30 days prior to screen). Particular caution will be paid to individuals taking Lithium or corticosteroids, but they will not be excluded from the study.

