Fluid Retention Edema, capillary leak syndrome, pleural and/or pericardial effusion have been reported in patients after LEUKINE administration. In 156 patients enrolled in placebo-controlled studies using LEUKINE at a dose of 250 mcg/m²/day by 2-hour IV infusion, the reported incidences of fluid retention (LEUKINE vs. placebo) were as follows: peripheral edema, 11% vs. 7%; pleural effusion, 1% vs. 0%; and pericardial effusion, 4% vs. 1%. Capillary leak syndrome was not observed in this limited number of studies; based on other uncontrolled studies and reports from users of marketed LEUKINE, the incidence is estimated to be less than 1%. In patients with preexisting pleural and pericardial effusions, administration of LEUKINE may aggravate fluid retention; however, fluid retention associated with or worsened by LEUKINE has been reversible after interruption or dose reduction of LEUKINE with or without diuretic therapy. LEUKINE should be used with caution in patients with preexisting fluid retention, pulmonary infiltrates or congestive heart failure.

Respiratory Symptoms Sequestration of granulocytes in the pulmonary circulation has been documented following LEUKINE infusion¹² and dyspnea has been reported occasionally in patients treated with LEUKINE. Special attention should be given to respiratory symptoms during or immediately following LEUKINE infusion, especially in patients with preexisting lung disease. In patients displaying dyspnea during LEUKINE administration, the rate of infusion should be reduced by half. If respiratory symptoms worsen despite infusion rate reduction, the infusion should be discontinued. Subsequent IV infusions may be administered following the standard dose schedule with careful monitoring. LEUKINE should be administered with caution in patients with hypoxia.

Cardiovascular Symptoms Occasional transient supraventricular arrhythmia has been reported in uncontrolled studies during LEUKINE administration, particularly in patients with a previous history of cardiac arrhythmia. However, these arrhythmias have been reversible after discontinuation of LEUKINE. LEUKINE should be used with caution in patients with preexisting cardiac disease.

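### The medial temporal atrophy (MTA) hypothesis is pointed at an on-drug MRI about 18 days after the first dose, and the analysis section names no scan, so a gain there is ambiguous and a null says almost nothing

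*Combined protocol and SAP*

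**What the plan says.** Hypothesis 3 (Specific Aim 3, the tertiary endpoint) is that treatment "will reverse or stop the progression of MTA".

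The relevant scans are described in several places:

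- **Screening MRI.** Study Events: "A brain MRI will also be done during the screening period". On the baseline visit, the same section says "This visit takes place about 1 to 4 weeks after the screen visit".
- **Day 15 MRI.** Study Events, last treatment visit: "A brain MRI will be done for comparison with the initial screen MRI to assess for any changes in the Medial Temporal lobe". The same sentence has that scan checked for vasogenic edema and microhemorrhage. The study schedule marks both an injection and an MRI on Day 15. Dosing is "for 5 days/ week for three weeks" (Specific Aim 1), so Day 15 is the fifteenth injection day.
- **First follow-up MRI.** Study Events places it about 45 days after the last treatment visit, within a week either side, and states no purpose. Trial History explains its addition: "we included another brain MRI at the first follow-up visit, to further assess any evidence of ARIA at that time point". The PET Procedure section also ties the MRIs done alongside PET to ARIA, and uses the subject's MRI to reduce white-matter contamination of the SUVR.

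The Data Analysis Plan, Tertiary Endpoint, says: "Group comparisons of changes in regional volumes and thicknesses will be analyzed using a series of one-way analyses of variance". It does not say which MRI supplies the change. The attached product information, under Warnings, says: "Edema, capillary leak syndrome, pleural and/or pericardial effusion have been reported in patients after LEUKINE administration". It adds that fluid retention reversed after interruption or dose reduction.

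**The concern.** The only post-baseline scan that the protocol ties to medial temporal change is taken on a dosing day. Two readings of its result are then unsafe.

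First, if volumes rise in the active arm, the plan has no means at Day 15 of telling recovered tissue from a temporary effect of being on drug. The placebo arm does not help, because such an effect would be confined to the active arm. Hypothesis 3 would read the rise as reversal of atrophy, which is a disease-modification claim.

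Second, if the arms do not differ, that says almost nothing about progression, because the time on treatment is too short for untreated atrophy to open a visible gap.

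Because the analysis section names no scan, Day 15 or first follow-up could also be chosen as the MTA result after the data are seen. The off-drug scan that would help with the first problem is already being acquired.

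**Working it through.** **The plan's own figure.** The sample-size table gives 20 per group for d = 0.5, two-tailed, alpha 0.20, power 0.60. A two-sample t calculation gives 19.1, which rounds up to 20, so the figure reproduces. The table was built for cognition, and the 20 per arm is justified on safety. No interval, effect size or power is given for MRI. With 20 per arm the detectable standardised difference is d = 0.49 at alpha 0.20 and power 0.60, or d = 0.91 at two-sided alpha 0.05 and power 0.80.

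**Intervals.** Screening is 7 to 28 days before Day 1. Fifteen weekday injections from a Monday start span 18 calendar days (20 for any other weekday).

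- Screening to Day 15 MRI: 7 + 18 = 25 to 28 + 18 = 46 days (27 to 48 for another start day). It is shorter if the MRI falls late in screening.
- Day 1 to Day 15 MRI, the only part the drug can affect: 18 days.
- Day 1 to first follow-up MRI: 18 + 45 = 63 days (56 to 70 with the 7-day window).
- Screening to first follow-up MRI: 25 + 45 = 70 to 46 + 45 = 91 days (63 to 98 with the window).

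**Assumptions, not in the documents.** Untreated loss of 3-5% per year, and an SD of change of 1-3 percentage points.

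**Largest possible arm difference**, if atrophy stops completely on Day 1 and (for follow-up) stays stopped: rate × days since Day 1 / 365.25.

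- Day 15: 3 × 18/365.25 = 0.15 to 5 × 18/365.25 = 0.25 points.
- First follow-up: 3 × 63/365.25 = 0.52 to 5 × 63/365.25 = 0.86 points.

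**Power**, two-sample t test, two-sided alpha 0.05, with d = difference / SD. Trial History counts the cohorts remaining when the follow-up MRI was added as 10 active and 10 placebo, so follow-up uses 10 per arm.

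| Scan | n per arm | Worst case (3%, SD 3) | Best case (5%, SD 1) |
|---|---|---|---|
| Day 15 | 20 | d = 0.05, power 5% | d = 0.25, power 12% |
| First follow-up | 10 | d = 0.17, power 7% | d = 0.86, power 45% |

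For 80% power, Day 15 needs 0.91 × SD, that is 0.9 to 2.7 points, against at most 0.25 available. At follow-up with 10 per arm the detectable d is 1.32, that is 1.3 to 4.0 points, against at most 0.86.

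**A further inconsistency.** Specific Aims 1 and 2 count the 45-day assessments from the start of treatment, whereas Study Events counts 45 days from the last treatment visit. On the first reading the follow-up MRI falls 7 + 45 = 52 to 28 + 45 = 73 days after screening, and only 45 - 18 = 27 days after the last dose.

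**The case against.** Several stronger readings are tempting, and the documents do not support them.

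- *The follow-up MRI is reserved for ARIA.* It is not. The subject's MRI also serves PET quantification, the visit text gives the follow-up scan no exclusive purpose, and the Tertiary Endpoint analysis, by naming no time point, does not exclude it. What stands is that no section assigns it to MTA.
- *The drug is known to swell the brain.* The background sections attribute vasogenic edema to anti-amyloid immunotherapies; here it is looked for as a precaution. The product warning concerns edema, capillary leak and effusions, with comparative rates from intravenous infusion, whereas this trial doses subcutaneously. No section documents an effect on brain volume, and the protocol reports no onset of ARIA so far. A fluid effect is an unexcluded explanation, not a demonstrated one.
- *Stopped progression is impossible to detect.* That depends on atrophy rates and SDs from outside the documents. Very low power under stated assumptions is as far as it goes.
- *The whole screening-to-Day-15 interval counts.* Using all 25 to 46 days would give differences of 0.21 to 0.63 points and power up to about 49%, but the drug cannot slow loss before Day 1.

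It is also fair to say that MTA is a tertiary endpoint in a pilot sized for safety, that no decision rule uses it, and that the follow-up scan covers only about half the planned sample. Moving the whole conclusion to that scan would exchange an on-drug ambiguity for a smaller sample, and a null there would be just as uninformative. These points limit the weight of the concern and shape the remedy. They do not remove the ambiguity of a Day 15 gain or the open choice of scan.

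**Conclusion.** The concern holds in a limited form. The protocol narrative directs the MTA comparison to an on-drug scan with about 18 treatable days behind it, the analysis section leaves the scan unnamed, and the off-drug MRI is not assigned to MTA. A Day 15 gain cannot be separated from a temporary on-drug effect. Power for complete arrest is about 5-12% at Day 15 (20 per arm) and about 7-45% at first follow-up (10 per arm), conditional on the assumed 3-5% annual loss and SD of 1-3 points. A null at either time is not evidence about progression. The correction is inexpensive and worth making, but the primary and secondary endpoints are unaffected.

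**What to change.** In the Data Analysis Plan, Tertiary Endpoint:

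1. Replace the one-way ANOVAs on change with one repeated-measures model of all post-screening MRIs, with treatment by visit, and with actual days since the screening MRI and screening volume as covariates.
2. Report the Day 15 (on-drug) and first follow-up (off-drug) contrasts separately.
3. State that a Day 15 gain is not called reversal of atrophy unless it is also present at first follow-up.
4. State that a null result at either time point is not evidence about progression, and label MTA results hypothesis-generating.
5. Reconcile Specific Aims 1 and 2 with Study Events on whether the 45 days run from the start of treatment or from the last treatment visit.

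The cost is wording plus segmentation of scans already being acquired; no visit is added. The drawback is that the follow-up contrast rests on about 10 per arm. Because the amyloid PET entry criterion came in with the same amendment, those participants were also selected differently from the earlier ones, and the report should say so.
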